**Medtronic Confidential**

This document is electronically controlled

056-F275, v3.0 Clinical Investigation Plan Template

## 1. Investigator Statement

The Investigator Statement will be provided as a separate document.

## 2. Glossary

Below is a list of terms and definitions and/or acronyms used within this document.

Term	Definition
AE	Adverse Event
AVN	Atrioventricular Node
BBB	Bundle Branch Block
CIP	Clinical Investigation Plan
CRF	Case Report Form
CTA	Clinical Trial Agreement
CV	Curriculum Vitae
DD	Device Deficiency
e.g.	For example
eCRF	Electronic Case Report Form
EGM	Electrogram
EKG	Electrocardiogram
EP	Electrophysiology
GCP	Good Clinical Practice
HB	Bundle of His / His Bundle
HBP	His bundle pacing
HIPAA	Health Insurance Portability and Accountability Act
HV	His-Ventricular
IC	Informed Consent
ICF	Informed Consent Form
IPG	Implantable Pulse Generator

# Imaging Study of Lead Implant for His Bundle Pacing Clinical Investigation Plan

056-F275

Version 4.0

Page 9 of 57

Medtronic

Term	Definition
IRB	Institutional Review Board
LAO	Left Anterior Oblique (fluoroscopy view angle)
LV	Left Ventricle
MA	Medical Advisor
MedDRA	Medical Dictionary for Regulatory Activities
PCT	Pacing Capture Threshold
RA	Right Atrial
RAO	Right Anterior Oblique (fluoroscopy view angle)
RV	Right Ventricle
S-QRS	Stimulus to QRS
SAE	Serious Adverse Event
SAP	Statistical Analysis Plan
US	United States
V	Ventricle or Ventricular

---

**Medtronic Confidential**

This document is electronically controlled

056-F275, v3.0 Clinical Investigation Plan Template

# Imaging Study of Lead Implant for His Bundle Pacing Clinical Investigation Plan

056-F275

Version 4.0

Page 10 of 57

Medtronic

## 3. Synopsis

Title	Imaging Study of Lead Implant for His Bundle Pacing (IMAGE-HBP)
Product Name	Medtronic SelectSecure™ MRI SureScan™ Model 3830 pacing lead
Sponsor	Medtronic, PLC Cardiac Rhythm and Heart Failure Clinical Research [name] [name]
Investigation Purpose	The purpose of this research study is to assess the implant success proportion of the Medtronic SelectSecure™ MRI SureScan™ Model 3830 pacing lead at the bundle of His for His bundle pacing, evaluate implant lead electrical measurements and changes over time, estimate the correlation between lead location and selective vs. non-selective HBP, and estimate the correlation between long-term lead performance and implant characteristics. Data from the study may be used to standardize the implant workflow to help improve the ease and predictability of His bundle pacing implants.
Product Status	The IMAGE-HBP Study will be conducted using market released products. The implanted system will comprise of any market approved Medtronic implantable pacemaker, market approved Medtronic pacing lead for the right atrium (if applicable) and the Medtronic SelectSecure™ MRI SureScan™ Model 3830 pacing lead for His bundle pacing. The Medtronic SelectSecure™ MRI SureScan™ Model 3830 pacing lead is market approved for pacing and sensing in the atrium or ventricle.
Primary Objective(s)	Assess the implant success proportion of the Medtronic SelectSecure™ MRI SureScan™ Model 3830 pacing lead at the bundle of His for His bundle pacing. 

Implant success will be defined as the presence of a H wave on the implanted lead electrogram and a His bundle pacing capture threshold equal to or less than 2.5V at 1.0ms.

Secondary Objective(s)	The secondary objectives are descriptive in nature and are intended to provide additional information about His bundle pacing with the Medtronic SelectSecure™ MRI SureScan™ Model 3830 lead. There will be no established performance requirements for these secondary objectives.

**Medtronic Confidential**

This document is electronically controlled

056-F275, v3.0 Clinical Investigation Plan Template

# Imaging Study of Lead Implant for His Bundle Pacing Clinical Investigation Plan

056-F275

Version 4.0

Page 11 of 57

Medtronic

	

• Estimate the correlation between lead position and selective vs. non-selective His bundle pacing occurrence at implant

• Assess changes in lead electrical measurements over time

• Assess changes in QRS duration over time

• Estimate the correlation between implant characteristics and long-term lead electrical performance at 12 months

• Characterize the occurrence of complications related to the procedure or lead for His bundle pacing up to 12 months

Study Design	
This is a prospective, non-randomized, multi-site, clinical research study.
 
All subjects included in the study will be implanted with a Medtronic market released de novo Implantable Pacemaker, Medtronic SelectSecure™ MRI SureScan™ Model 3830 lead at the bundle of His for His bundle pacing, and compatible market released Medtronic Right Atrial lead (if applicable). The subjects with an implant of the Medtronic SelectSecure™ MRI SureScan™ Model 3830 lead for His bundle pacing will undergo a Cardiac CT Scan and be followed up to twelve months post implant for electrical testing. Subjects that do not receive an implanted SelectSecure™ MRI SureScan™ Model 3830 pacing lead for His bundle pacing will be exited from the study at the time of the unsuccessful implant or after any reportable Adverse Events are resolved.

Sample Size	
Up to 70 patients will be enrolled to ensure approximately 62 patients undergo an implant procedure.
 

• A sample size of 62 patients (who undergo an implant procedure) will produce a two-sided 95% confidence interval with a width equal to 0.15 for the implant success proportion when the observed implant success proportion is 0.9.

Inclusion/Exclusion Criteria	
The following is a list of inclusion/exclusion criteria:
 
Inclusion criteria
 

• Subject has a Class I or II indication for implantation of an implantable pacemaker

• Subject (or legally authorized representative) has signed and dated the study-specific Consent Form

• Subject is 18 years of age or older, or is of legal age to give informed consent per local and national law

• Subject is expected to remain available for follow-up visits

 
Exclusion criteria

**Medtronic Confidential**

This document is electronically controlled

056-F275, v3.0 Clinical Investigation Plan Template

# Imaging Study of Lead Implant for His Bundle Pacing Clinical Investigation Plan

056-F275

Version 4.0

Page 12 of 57

Medtronic

	

• Subject is contraindicated for Cardiac CT

• Subject has an existing or prior pacemaker, ICD or CRT device implant

• Subject is intended to receive an implant of a Left Ventricle lead or CRT device

• Subject life expectancy is less than 1 year

• Pregnant women or breastfeeding women, or women of child bearing potential and who are not on a reliable form of birth regulation method or abstinence

• Subjects with exclusion criteria required by local law (e.g. age or other)

• Subject with a medical condition that precludes the patient from participation in the opinion of the investigator

• Subject is enrolled in a concurrent study that may confound the results of this study. Co-enrollment in any concurrent clinical study (including registries) requires approval of the study manager or designee.

Study Procedures and Assessments	
Enrollment/Baseline
 

• Eligibility Verification

• Informed Consent

• Demographics

• Primary Indication for implant

• Medical History

 
Implant
 

• Implant tools used

• His mapping testing

• Implant procedure times

• Final lead electrical testing

• Final system configuration

• EKG measurements

• Fluoroscopy Cine images

• Physician Questionnaire

 
Pre-hospital discharge
 

• Electrical lead testing

• EKG rhythm strips and measurements

 
Cardiac CT Scan
 

• Cardiac CT Scan images

 
1 week, 3 month, 6 month, 12 month Follow-up

---

**Medtronic Confidential**

This document is electronically controlled

056-F275, v3.0 Clinical Investigation Plan Template

	

• Electrical lead testing

• Electrical lead testing with strength duration (3 month only)

• DR220 Holter monitor (1 week and 3 or 6 month)

• EKG rhythm strips and measurements

 
Adverse Events/Device Deficiency
 

• Description

• Diagnostic tests and procedures

• Actions taken

• Relatedness and Classifications

• Outcome

 
System Modification
 

• Reason for modification

• Final device information

• Final lead electrical testing

• EKG printouts and measurements

 
Protocol Deviation
 

• Description

• Reason

 
Study Exit
 

• Reason for exit

• Lost to follow-up

Safety Assessments	Device Deficiencies and Adverse Events related to the procedure or Medtronic SelectSecure™ MRI SureScan™ Model 3830 pacing lead for His bundle pacing will be collected. In addition, all SAEs that result in death will be collected.
Statistics	The estimated implant success proportion will be calculated as the proportion of all subjects who undergo an implant attempt that is successful. A 95% confidence interval for the proportion of successful implants will be constructed using the Wilson method.

## 4. Introduction

### 4.1. Background

The human cardiac conduction system is admirably suited to deliver coordinated electrical impulses that result in synchronous and mechanically efficient ventricular myocardial contraction. Pacing stimulation at the bundle of His (HB), which conducts through the Purkinje system is fundamentally different than a myocardial stimulation elsewhere in the right ventricle (RV) which results in abnormal physiology. Indeed, chronic right ventricular apical pacing may be associated with increased risk of death, heart failure, hospitalization, and the development of persistent atrial fibrillation.

# Imaging Study of Lead Implant for His Bundle Pacing Clinical Investigation Plan

056-F275

Version 4.0

Page 14 of 57

Medtronic

The bundle of His, or common atrioventricular (AV) bundle, consists of specialized myocardial cells located distal to the atrioventricular node (AVN). The HB acts as a conduit between the atrium and the ventricles, transmitting depolarization from the AVN through the fibrous skeleton to the right and left bundle branches and ultimately the Purkinje system^6.

Permanent pacing of the HB to restore the native intrinsic AV conduction system continues to gain popularity with implanters. Over the last two decades several investigators reported experience with permanent His bundle pacing (HBP) resulting in paced QRS morphology similar to an intrinsically conducted beat. These clinical data showed HBP was feasible and associated with improvement in left ventricular dimensions, functional status, cardiothoracic ratio, and ejection fraction. Reaching the targeted implant area for HBP remains technically challenging because of the lack of anatomical and electrical markers used to facilitate traditional lead implant. Paced QRS morphology is not sufficient to confirm successful HBP location and the fluoroscopic image may mislead the implanter to an undesirable pacing site. AV nodal, HB, AV septal and proximal bundle branch pacing may result in the same QRS morphology but completely different electrical performance (**Figure 1**).

Definitions for Selective HBP and Non-Selective HBP are separated based on the patient's intrinsic QRS morphology and determined by electrocardiogram (EKG) identifiers and pacing capture thresholds (PCT). **Table 1** provides the definitions for Selective and Non-Selective HBP for patients with initial normal QRS and patients with a bundle branch block (BBB).

**Table 1: Definitions for His Bundle Pacing**

	Normal QRS	Bundle Branch Block #	
		With correction*	Without correction
Selective HBP	

• S-QRS = HV with isoelectric interval

• Discrete local V electrogram in HBP lead with S-V=H-V

• Paced QRS = native QRS

• Single capture thresholds (His bundle)

	

• S-QRS <math>\leq</math> H-QRS with isoelectric interval

• Discrete local V electrogram in HBP lead

• Paced QRS < native QRS

• 2 distinct capture thresholds (HBP with BBB correction, HBP without BBB correction)

	

• S-QRS <math>\leq</math> or <math>></math> H-QRS with isoelectric interval

• Discrete local V electrogram in HBP

• Paced QRS = native QRS

• Single capture threshold (HBP with BBB)

# Imaging Study of Lead Implant for His Bundle Pacing Clinical Investigation Plan

056-F275

Version 4.0

[figure not shown]
Page 15 of 57

Medtronic

Non-Selective HBP	
 
• S-QRS < H-QRS (usually 0, S-QRSend = H-QRSend) with or without isoelectric interval (Pseudodelta wave +/-)
 
• Direct capture of local V electrogram in HBP lead by stimulus artifact (local myocardial capture)
 
• Paced QRS > native QRS with normalization of precordial and limb lead axes with respect to rapid dV/dt components of the QRS
 
• 2 distinct capture thresholds (HBP capture, RV capture)
 
	
 
• S-QRS < H-QRS (usually 0, S-QRSend < H-QRSend) with or without isoelectric interval (Pseudodelta wave +/-)
 
• Direct capture of local V electrogram in HBP lead by stimulus artifact
 
• Paced QRS <math>\leq</math> native QRS
 
• 3 distinct capture thresholds (HBP with BBB correction, HBP without BBB correction, RV capture)
 
	
 
• S-QRS < H-QRS (usually 0) with or without isoelectric interval (Pseudodelta wave +/-)
 
• Direct capture of local V electrogram in HBP lead by stimulus artifact
 
• Paced QRS > native QRS
 
• 2 distinct capture thresholds (HBP with BBB, RV capture)
 

--------------------------	--------------------------------------------------------------------------------------------------------------------------------------------------------------------------------------------------------------------------------------------------------------------------------------------------------------------------------------------------------------------------------------------------------------------------------------------------------------------------------------------------------------------	-------------------------------------------------------------------------------------------------------------------------------------------------------------------------------------------------------------------------------------------------------------------------------------------------------------------------------------------------------------------------------------------------------------------------------------------	-----------------------------------------------------------------------------------------------------------------------------------------------------------------------------------------------------------------------------------------------------------------------------------------------------------------------------------------

# including infra-nodal AV block; \* Narrowing of QRS

S-QRS stimulus to QRS; V ventricular; BBB bundle branch block; RV right ventricle; HBP His bundle pacing

**Figure 1: His Bundle Anatomy**

Compact AV node (1) converges into a transitional zone (2) before continuing as the His bundle (3) at the apex of triangle of Koch. The His bundle penetrates the membranous septum and continues as bundle branches (4) on the summit of muscular septum.

To address the clinical challenges, the IMAGE-HBP study will seek to evaluate and understand the correlation between implant electrical performance, lead implant location and chronic HBP lead electrical performance.

Additionally, the IMAGE-HBP study will look to identify a correlation between anatomical landmarks and the electrical signature of HBP, which may allow investigators to refine an implant flowchart and lead to a better understanding of use conditions of both implant tools and leads during an implant for HBP.

Therefore, the IMAGE-HBP study will collect data to help improve the ease and predictability of the implant and improve electrical performance of HBP.

## 4.2. Purpose

The IMAGE-HBP Study is a prospective, non-randomized, multi-site, clinical research study.

The purpose of this research study is to assess the implant success proportion of the Medtronic SelectSecure™ MRI SureScan™ Model 3830 pacing lead at the bundle of His for His bundle pacing, evaluate implant lead electrical measurements and changes over time, evaluate changes in QRS duration over time, estimate the correlation between lead location and selective vs. non-selective HBP, and estimate the correlation between long-term lead performance and implant characteristics. Data from the study may be used to standardize the implant workflow to help improve the ease and predictability of His bundle pacing implants.

## 5. Objectives and Endpoints

### 5.1. Objectives

#### 5.1.1. Primary Objective

The primary objective is to assess the implant success proportion of the Medtronic SelectSecure™ MRI SureScan™ Model 3830 pacing lead at the bundle of His for His bundle pacing. Implant success will be defined as the presence of a H wave on the implanted lead EGM and a HB pacing capture threshold equal to or less than 2.5V at 1.0ms.

#### 5.1.2. Secondary Objectives

The secondary objectives are descriptive in nature and are intended to provide additional information about HBP with the SelectSecure™ MRI SureScan™ Model 3830 pacing lead. There will be no established performance requirements for these secondary objectives.

- Estimate the correlation between the lead position and selective vs. non-selective HBP occurrence at implant
- Assess changes in lead electrical measurements over time
- Assess changes in QRS duration over time
- Estimate the correlation between implant characteristics and long-term lead electrical performance at 12 months
- Characterize the occurrence of complications related to the procedure or lead for His bundle pacing up to 12 months

### 5.1.3. Ancillary Objectives

Additional analyses may be done on data and images collected during the study as outlined below. These analyses are descriptive in nature and are intended to provide additional information about His bundle pacing with the Medtronic SelectSecure™ MRI SureScan™ Model 3830 lead.

- To characterize performance of existing delivery tools and Medtronic SelectSecure™ MRI SureScan™ Model 3830 lead for HBP
- To summarize implant procedure information
- To characterize the survival for subjects up to 12 months post-implant.

## 6. Study Design

The Imaging Study of Lead Implant for His Bundle Pacing (IMAGE-HBP) is a prospective, non-randomized, multi-site, clinical research study. The purpose of this research study is to assess the implant success proportion of the Medtronic SelectSecure™ MRI SureScan™ Model 3830 pacing lead at the bundle of His for His bundle pacing, evaluate implant lead electrical measurements and changes over time, evaluate changes in QRS duration over time, estimate the correlation between lead location and selective vs. non-selective HBP, and estimate the correlation between long-term lead performance and implant characteristics. Data from the study may be used to standardize the implant workflow to help improve the ease and predictability of His bundle pacing implants.

All subjects included in the study will be implanted with a Medtronic market released de novo implantable pacemaker, Medtronic SelectSecure™ MRI SureScan™ Model 3830 lead for HBP, and compatible market released Medtronic Right Atrial lead (if applicable). The subjects with an implant of the Medtronic SelectSecure™ MRI SureScan™ Model 3830 lead for HBP will undergo a Cardiac CT Scan and be followed up to twelve months post implant for electrical testing. Subjects that do not receive an implanted SelectSecure™ MRI SureScan™ Model 3830 pacing lead for HBP will be exited from the study at the time of the unsuccessful implant or after any reportable AEs are resolved.

An unsuccessful implant is not considered an adverse event; however any adverse events occurring during an unsuccessful implant attempt (e.g. perforation) must be evaluated for reporting.

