## 9.4. Enrollment

The point of enrollment is defined as the time at which a patient has signed and dated the ICF. The date the subject signed (or legally authorized representative) the ICF and data protection authorization, as required by law, must be documented in the subject's medical records. At that point, the patient is considered a subject in the study, a study subject ID number will be assigned, and the subject must be followed through their 12 month post-implant clinic visit unless the subject exits the study prior to study closure. Once informed consent is obtained, report AEs/deaths, study deviations and subject exits as they occur.

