## 9.11. Subject Withdrawal or Discontinuation

Study exit is defined as the moment when a subject officially stops participating in the study. From that moment onward no data will be collected from the subject. The date and the reason for exiting the subject must be reported to Medtronic at the earliest opportunity.

Subjects will be exited from the study for any of the following situations:

- Study completed
- Subject does not have an implant of a SelectSecure™ MRI SureScan™ 3830 lead for His bundle pacing
- Subject death
- Subject lost to follow-up
- Subject did not meet eligibility criteria
- Subject chooses to exit
- Investigator withdraws subject

If possible, the following procedures should be performed / data collected at the exit visit:

- Report the reason for exit
- Final interrogate ALL and save-to-media file for exits occurring prior to the 12 month visit
- Adverse Events
- Study deviations
- Device Deficiencies

Following exit, subjects will continue to receive standard medical care. There will be no further required study-related follow-up visits for these subjects. All data through the time of the subject's exit will be available for data analyses.

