7.1.3. Analysis Sets

There will be two analysis sets used in this study:

Analysis Set #1:

This analysis set will be used for the primary objective (implant success), secondary objective #5 (adverse events), and ancillary objectives #1 and #2. Study subjects will be included in this analysis set if an implant is attempted.

A STROBE flow diagram per section 7.1.1 will outline the specific exclusions.

Analysis Set #2:

This analysis set will be used for secondary objectives #1-#4 and ancillary objective #3. Study subjects will be included in this analysis set if they have a successful implant.

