7.9.6. Secondary Objective #5

This secondary objective is to characterize the occurrence of any complications related to the procedure or the lead for His bundle pacing up to 12 months post-implant.

Analysis Dataset:

Analysis set #1 per section 7.1.3.

Analysis Method:

The types of complications related to the procedure or the lead for His bundle pacing will be summarized using frequencies and percentages. The probability of a subject being free of a complication related to the procedure or the lead for His bundle pacing through 12 months post-implant will be estimated using the Kaplan-Meier method.

The Kaplan-Meier analysis will be performed in SAS using code similar to:

```
proc lifetest data=analysisset1 conftype=loglog timelist=12;
  time monthsEvent*event(0);
run;
```

In addition, the relationship between implant characteristics, including lead position, HB PCT at implant, and QRS duration at implant, and the occurrence of complications related to the procedure or the lead for His bundle pacing will be assessed using a Cox proportional hazard regression model. The Cox proportional hazards analysis will be performed in SAS using code similar to:

```
proc phreg data=analysisset;
  class leadloc;
  model monthsEvent*event(0) = leadloc pct0 pacedqrs0;
run;
```

Endpoint Definition:

Procedure and the lead for His bundle pacing related complications will be reported via the Adverse Event eCRF. Examples include but are not limited to: lead dislodgement, exit block, loss of capture, or high threshold causing action.

Additional Analysis:

All adverse events collected in the study will be characterized. A table with MedDRA Preferred terms will be generated, which will report for each MedDRA Preferred term, the number of adverse events, the number of subjects with event, and these numbers also restricted to complications. This table will be similar to:

Table 2. MedDRA terms

MedDRA Preferred Term	Adverse events		Complications	
	lead related	procedure related	lead related	procedure related
Exit block	1 (1)	0 (0)	0 (0)	0 (0)
High threshold	1 (1)	0 (0)	1 (1)	0 (0)

MedDRA Preferred Term	Adverse events		Complications	
	lead related	procedure related	lead related	procedure related
Lead dislodgment	2 (2)	0 (0)	1 (1)	0 (0)
Loss of capture	4 (3)	1 (1)	2 (2)	0 (0)

A listing of all adverse events will be generated, with subject identifier, time of event relative to the implant procedure, event description, classification, outcome and MedDRA Preferred term.

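### Subjects left without a His bundle lead exit at the failed attempt, so the all-attempt 12-month complication estimate cannot see procedure complications that appear later in them

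*Protocol*

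**What the plan says.** Under protocol section 6, repeated in the synopsis and in SAP section 5, subjects who do not get the 3830 lead for HBP "will be exited from the study at the time of the unsuccessful implant or after any reportable AEs are resolved". Section 9.11 lists the same situation among its reasons for exit: "Subject does not have an implant of a SelectSecure™ MRI SureScan™ 3830 lead for His bundle pacing". On what follows exit, that section is explicit: "From that moment onward no data will be collected from the subject". It adds: "There will be no further required study-related follow-up visits for these subjects".

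The general follow-up duty in section 9.4 gives way to exit: "the subject must be followed through their 12 month post-implant clinic visit unless the subject exits the study prior to study closure". Section 9.8 calculates visit windows only once an index HBP lead implant has been reported, so a failed attempt generates no discharge or 1-week window. For the failed attempt itself, section 6 requires that "any adverse events occurring during an unsuccessful implant attempt (e.g. perforation) must be evaluated for reporting".

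SAP 7.1.3 assigns secondary objective #5 to Analysis Set #1 and defines membership thus: "Study subjects will be included in this analysis set if an implant is attempted". SAP 7.9.6 runs the 12-month Kaplan-Meier analysis on that set ("proc lifetest data=analysisset1 conftype=loglog timelist=12"). It pools procedure-related and lead-related complications and reports adverse events in unsuccessful implants separately. Neither document says how subjects without a lead are censored.

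**The concern.** The analysis population and the follow-up do not match. Every subject with an attempt counts in the 12-month estimate, but one who leaves the procedure without a lead and without an open adverse event contributes essentially no time at risk. A procedure complication that shows itself hours or days later in such a subject has no planned route into the data. Separate reporting of events in unsuccessful implants cannot recover what was never collected, and the same applies to the listing of deaths among all enrolled subjects in SAP 7.9.9.

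Kaplan-Meier then carries these subjects forward at the later hazard of the implanted subjects. They have no HBP lead to dislodge or lose capture, and their risk of delayed procedural complications may differ. The SAP already restricts its other 12-month time-to-event objective, survival, to successful implants. Objective #5 is different because it joins two kinds of complication that have different natural populations.

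At stake is the completeness of the procedure-safety data, and what a figure presented for all attempts actually describes.

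**Working it through.** **Inputs.** From the protocol (13.1.3 and Table 8): 62 attempts, planning success proportion 0.90, range 0.82 to 0.95. The complication risks below are assumptions, because the documents give none.

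**1. The plan's own figure.** Wilson width = 2z√[p(1−p)/n + z²/(4n²)] / (1 + z²/n). With n = 62, p = 56/62 and z = 1.96, the width is 0.1504, matching the stated 0.15. The other Table 8 rows reproduce with 59, 57, 54 and 51 successes, so whole-number counts are a fair basis for what follows.

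**2. Number affected.** Endpoint failures are 62 − 56 = 6 (9.7%) at 0.90, 62 − 59 = 3 (4.8%) at 0.95 and 62 − 51 = 11 (17.7%) at 0.82. These are upper bounds. Table 8 concerns the primary endpoint (H wave plus threshold), while exit applies to subjects with no HBP lead. A subject with the lead in place who misses the endpoint is not clearly exited.

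**3. Kaplan-Meier bias.** Assume exit means censoring on the procedure day, every endpoint failure has no lead, and implanted subjects are fully followed. For events after that day:

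bias = failed share × (risk in implanted − risk in failed)

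With 5% risk in implanted subjects, planned estimate of the complication probability minus the full-follow-up value, in percentage points:

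| Risk in failed attempts | 3 of 62 | 6 of 62 | 11 of 62 |
|---|---|---|---|
| 0% | +0.2 | +0.5 | +0.9 |
| 5% | 0 | 0 | 0 |
| 10% | −0.2 | −0.5 | −0.9 |
| 20% | −0.7 | −1.5 | −2.7 |
| 30% | −1.2 | −2.4 | −4.4 |

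For example, 6/62 × (0.05 − 0.30) = −0.024.

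**4. Chance of losing an event.** Among 6 subjects the chance of at least one unseen event is 1 − (1 − q)⁶: 26% at q = 5%, 47% at 10% and 74% at 20%.

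**5. Worked example (assumed counts).** Three later events are seen among 56 implanted subjects and one is missed among 6 failed attempts. The planned estimate is 3/56 = 5.4%; full follow-up gives 4/62 = 6.5%. The shortfall is 1.1 points, or 17% of 6.5%.

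**6. Why the censoring rule matters.** With the same three events, censoring the 6 on the procedure day gives 3/56 = 5.4%, and so does excluding them under the missing-data rule in SAP 7.4. Treating them as event-free to 12 months gives 3/62 = 4.8%. The SAP does not choose between these.

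**The case against.** The documents already cover part of this. Events during a failed attempt must be evaluated, a subject with a reportable event stays until it resolves, and section 9.11 asks for adverse events at exit where possible. Keeping every attempt in Set #1 is right for acute procedural events, and the separate table lets a reader see the failed-attempt group. Protocol Table 4 limits procedure-related events to those directly tied to implanting or surgically modifying the HBP lead, so few delayed events would qualify. Retaining subjects because they had an event also does little harm here: follow-up after a first complication does not alter a time-to-first-complication curve. Finally, the objective is descriptive with no performance requirement, and the products are market released.

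All of this stands, and it keeps the point small. It does not close the gap, because nothing restores observation between exit and the time when a delayed complication would appear.

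**Conclusion.** The mismatch is real and its effect is modest. Two parts follow from the text alone: complications first appearing after exit cannot be recorded, and the later part of the all-attempt curve rests essentially on implanted subjects. The reach is at most about 6 of 62 subjects at the planning rate. The direction and size of bias rest on assumed risks and on the inferred censoring.

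A reader might infer more, and the documents do not support it:

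- **The estimate is tilted favourably.** The sign depends on which group has the higher risk; with equal risks there is no bias, only lost information.
- **Failed attempts carry the highest risk, after longer procedures with more fixation attempts.** This is plausible, but neither document gives a figure for it.
- **One missed event in four understates the rate by a quarter.** That holds for a crude percentage over 62 (3/62 against 4/62), not for the planned Kaplan-Meier estimate.
- **Six subjects will certainly have no follow-up.** Six is the ceiling at 0.90, for the reason in step 2.

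This is a worthwhile low-cost improvement, and it does not threaten the primary objective.

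**What to change.** Amend the exit wording in protocol sections 3, 6 and 9.11, and in SAP section 5, so that subjects without an HBP lead remain on study for adverse-event ascertainment only. Use the end of the existing 1-week window (day 17, protocol Table 3) as the limit, with chart review or a telephone call as the method.

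In SAP 7.9.6:

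- report procedure-related complications over that window as a proportion of all attempts;
- report lead-related complications to 12 months by Kaplan-Meier in subjects with an implanted HBP lead;
- state the censoring rule.

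The cost is a protocol amendment, which section 15.6 makes subject to investigator, sponsor and IRB approval, plus one contact or chart check each for about 6 subjects or fewer. No treatment, clinic visit, procedure or staffing changes. If the amendment is not made, the SAP changes to the 12-month population and the censoring rule can still be adopted. The analysis would then describe its population correctly, but the unseen events would stay unseen.
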